4.2. Scientific Rationale for Study Design

The primary goal of this study is to assess the tolerability of D/C/F/TAF FDC in HIV-1 infected participant who are virologically-suppressed suppressed (HIV-1 RNA <50 copies/mL) and have experienced rapid and significant body weight gain on an INI + TAF/FTC ARV regimen.

Blinding, Control, Study Phase/Periods, Intervention Arms

An active control will be used to determine treatment effects in this study. Continuation of the current ARV regimen consisting of an INI + TAF/FTC was chosen as the active control as this study evaluates the impact of switching from an INI + TAF/FTC ARV regimen to D/C/F/TAF FDC on body weight relative to continuation of the baseline INI + TAF/FTC ARV regimen. Given possible changes in weight when switching ARV regimens, it is important to understand the implications of not switching regimens and any difference in weight change among a control group.

This study will not be blinded as eligible participants may be receiving multiple INI + TAF/FTC based ARV regimens. Some regimens may be multiple tablet regimens or single tablet regimens of different sizes. Creating identical placebos for all possible regimens included in the active control arm is not considered appropriate because this would result in an increased pill burden, loss of convenience, and ease of adherence for participants who are accustomed to a simplified regimen.

Randomization will be used to minimize bias in the assignment of participants to treatment arms, to increase the likelihood that known and unknown participant attributes (eg, demographic or baseline characteristics) are evenly balanced across treatment arms, and to enhance the validity of statistical comparisons across treatment arms.

Two stratification factors (sex [Male or Female] and race [Black/African American or Non-Black/African American] at Baseline) will be applied in the randomization process. These stratification factors were chosen as previous studies have identified these populations being at an increased risk of weight gain while taking an INI-based ARV regimen, therefore a need to ensure equal distribution across the treatment arms.

Primary Analysis Time Point and Study Period

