9.4.2. Primary Analysis

The primary endpoint analyses will be based on the ITT population. The analysis will be conducted using linear mixed-effects model with participant as random effect adjusted by baseline BMI and stratification factors in a longitudinal data with repeated measures (percent body weight change measured at multiple visits).⁴⁰

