1.5. Sample Size Justification

[figure not shown]
Using a T-test with 80% power to detect a difference of 3% at the significance level of 0.05, 2-sided, the sample size per treatment arm is a simple function of effect size (ES): $n_{arm}=16/(ES)^2$. The effect size is the standardized difference: $ES=\Delta/\sigma$, where Δ is the difference between the two arms, and σ^2 is the common variance. Since there was no direct data on the study population to assume the observed difference, Δ =3% is considered a clinical meaningful difference. Internal data from 2 Phase 3 studies^{2, 3} on D/C/F/TAF FDC arm from different HIV patient populations (naive, switch) have shown the %body weight change in the range of 1.5% to 1.8% and standard deviation from 4.0 to 4.6 (Table 1 and Figure 2), resulting a range of ES and corresponding sample size³.

Table 2 Phase 3 Studies on D/C/F/TAF FDC Arm

Study	AMBER D/C/F/TAF arm	EMERALD D/C/F/TAF arm
N % body weight change from baseline at week 24 (SD)	347 1.5 (4.6)	738 1.8 (4.0)
N % body weight change from baseline at week 48 (SD)	340 2.3 (5.0)	728 1.9 (5.1)

(Data on file)

Figure 2: Sample Size Estimation by Treatment Effect Size

Given the uncertainty of either the Δ or the variability, an adaptive unblinded SSR is planned to reestimate the sample size in an IA to ensure adequate power in the hypothesis testing for the primary endpoint using the conditional power approach. An initial sample size of 55 participants per treatment arm (110 participants total) will be used for treatment effect size of 0.54 (ADDPLAN version 6). The IA is planned when approximately 60% of the initial planned 110 participants have completed the Week 12 visit and approximately 30% of participants have completed the Week 24 visit to re-estimate the sample size to ensure adequate power for the hypothesis testing. All cumulative data will be used for the IA. The planned maximum total sample size after SSR is 150 participants. Details for the SSR,

threshold for the conditional power, and protection of overall significance level will be provided in the statistical plan for the IA and monitoring.

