1.6. Randomization and Blinding

1.6.1. Procedures for Randomization

Participants will be randomly assigned to one of two intervention arms based on a computer-generated randomization schedule prepared before the study by or under the supervision of the sponsor. Randomization will be based on a computer-generated schedule, constructed via random permuted blocks to ensure balance across treatment arms in each strata of the stratification factors (sex and race), and prepared before the start of the study by the sponsor.

Central randomization will be implemented in this study. Participants will be randomized in a 1:1 ratio to the Immediate Switch Arm (D/C/F/TAF FDC starting on Day 1 for 48 weeks), or the Delayed Switch Arm (continue current INI + TAF/FTC ARV regimen for 24 weeks then switch to D/C/F/TAF for an additional 24 weeks).

Randomization will be stratified by sex (Male or Female) and race (Black/African American or Non-Black/African American) at Baseline. A maximum enrollment of approximately 70% male participants will be utilized to ensure adequate recruitment of female participants. A maximum enrollment of approximately 70% non-black participants will be utilized to ensure adequate recruitment of diverse races.

The randomization and baseline visit (Day 1) cannot proceed until the investigator has received all results of the screening visit and participant eligibility has been confirmed in interactive web response system (IWRS), which should occur within approximately 30 days after the screening visit (for further details, see Section 8 in Protocol). It is the responsibility of the investigator to ensure that the participant is eligible for the study prior to enrollment. Randomization should be performed on the same day as the baseline visit (Day 1), provided that all screening procedures have been completed and participant eligibility has been confirmed.

The IWRS will assign open-label kit numbers at each study visit. Study drug will be dispensed to the participant in an open-label fashion. The requestor must use his or her own user identification and personal identification number when contacting the IWRS, and then will give the relevant participant details to uniquely identify the participant.

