5.2.3. Analysis Methods

The statistical hypothesis is the following:

 H_0 : Dt-Dc=0 versus H_1 : Dt -Dc \neq 0.

Where H₀ is the null hypothesis, H₁ is the alternative hypothesis; Dt= percent change in body weight at Week 24 from Baseline for D/C/F/TAFFDC (Immediate Switch Arm), Dc = percent change in body weight at Week 24 from Baseline for active control (Delayed Switch Arm).

The statistical hypothesis will be tested using mixed model for repeated measures (MMRM) below.

Y = Baseline BMI + Sex + Race + Time + Treatment + Treatment*Time + Subject + E

In this model, Y is the %change in body weight from baseline at time week 4, week 12, and week 24; baseline BMI, sex, race, time, treatment and treatment*time are fixed effects; subject is a random effect; and E is the random error. Subject is treated as a random effect to incorporate the variability and correlation among repeated measures (time).

The statistical hypothesis will be tested by estimating the treatment LSmeans for the %change in body weight corresponding to the time measurement at week 24. The significance level p-value and 95% confidence interval for the difference will be provided.

To control for the overall Type I error rate at the 2-sided 0.05 significance level, the weighted inverse-normal p-value combination test will be used to combine p-values from interim stage and primary analysis stage⁴. The overall p value will be calculated by the combination statistic below

$$Z(p_1,\,p_2) = \text{w1}\ \Phi^{-1}(1 - p_1) + \text{w2}\ \Phi^{-1}(1 - p_2)$$

where $w_1=\sqrt{(n_1/N)}$, $w_2=\sqrt{(n_2/N)}$, n_1 and n_2 are number of subjects in IA stage and remaining primary stage.

All available data from randomized participants that have received at least one dose is included (ITT analysis set) will be used for the analysis, regardless of the occurrence of intercurrent events.

Missing Data for body weight is assumed as Missing At Random (MAR). In addition, as a sensitivity analysis, a control-based multiple imputation will be applied to the MMRM model, assuming weight data is not missing at random.

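### The primary model adjusts the Week 24 contrast by covariate effects averaged over Weeks 4, 12 and 24; covariate-by-visit terms would give a small precision gain at almost no cost

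*SAP*

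**What the plan says.** SAP 5.2.3 gives the model as "Y = Baseline BMI + Sex + Race + Time + Treatment + Treatment*Time + Subject + E". The outcome is percentage weight change since baseline at Weeks 4, 12 and 24. Subject is random, E is random error, and every other term is fixed. The test is on the difference in Week 24 least-squares means.

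Protocol 9.4.2 describes the same structure: "participant as random effect adjusted by baseline BMI and stratification factors in a longitudinal data with repeated measures". SAP 1.4 agrees. SAP 5.2.3 also labels the model an MMRM, and SAP 5.2.4 reuses it for the sensitivity analyses. Neither section names a covariance matrix or visit-specific variances.

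Randomisation is 1:1, in permuted blocks stratified by sex and race (SAP 1.6.1). Protocol 4.2 explains the choice of strata: "previous studies have identified these populations being at an increased risk of weight gain while taking an INI-based ARV regimen".

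**The concern.** Percentage change is zero at Day 1 by construction, so any effect of BMI, sex or race on it has to build up after that. If it is still building between Weeks 4 and 24, a shared coefficient is too small for Week 24. The Week 24 contrast is then only partly adjusted, and variance that the covariates could have removed stays in the residual.

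What is at stake is precision in the trial's only hypothesis test. Randomisation keeps the treatment estimate unbiased whichever covariate terms are used.

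**Working it through.** **Plan's own figure.** SAP 1.5 sizes the trial as follows: "Using a T-test with 80% power to detect a difference of 3% at the significance level of 0.05, 2-sided"; the chosen sample size "will be used for treatment effect size of 0.54". Its rule gives 16/0.54² = 54.9, so 55 per arm. Exact t-test power at 55 per arm is 80.1% (80.8% by the normal approximation used below). The figure is reproduced. The implied SD is 3/0.54 = 5.56.

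**Weight of each visit in a shared coefficient.** Generalised least squares weights the visits by 1'V⁻¹/(1'V⁻¹1). A random intercept plus independent error gives equal variances and equal correlations, so the weights are 1/3, 1/3, 1/3 at any correlation. With an assumed 12% to 30% dropout by Week 24, the Week 4 weight rises only to 0.36–0.42.

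**Share of the gain kept.** Let c be the shared coefficient divided by the Week 24 coefficient. The share of covariate-explained Week 24 variance that is removed is 1 − (1 − c)².

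- Linear growth: c = (4 + 12 + 24)/3/24 = 0.556; share kept 1 − 0.444² = 80%.
- Square-root growth: c = (2 + 3.464 + 4.899)/3/4.899 = 0.705; share kept 91%.
- Constant effect: c = 1; share kept 100%.

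**Contrast case: visit-specific variances that rise.** For a random walk the weights are 1, 0, 0. Then c = 4/24 = 0.167 and the share kept is 31% under linear growth; under square-root growth c = 0.408 and the share is 65%. Across a range of unstructured matrices with rising SD, the Week 4 weight ran from about 0.5 to above 1, and the share kept under linear growth from 7% to 70%.

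**Power.** R² is the share of Week 24 variance explained jointly by the three covariates. The standard error is multiplied by √(1 − R² × share kept). Power is Φ(0.54/(√(2/55) × multiplier) − 1.96). Linear growth:

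| R² | Visit-specific effects | Shared effect, random intercept | Shared effect, random walk |
|---|---|---|---|
| 0.05 | 82.8% | 82.4% | 81.4% |
| 0.10 | 84.7% | 84.0% | 82.0% |
| 0.20 | 88.6% | 87.1% | 83.2% |
| 0.30 | 92.3% | 90.2% | 84.4% |

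Under the random intercept, the shared effect raises the standard error by 0.5%, 1.1%, 2.4% and 4.1% down the rows.

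For a random walk with square-root growth the losses are smaller. At R² 0.10 the multiplier is √(1 − 0.065) = 0.967 and power is 83.4% against 84.7%. At R² 0.20 it is √(1 − 0.13) = 0.933 and power is 85.9% against 88.6%.

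**Simulation checks (random-intercept data and fit).** In 150 trials per scenario with 110 participants, the fitted BMI coefficient equalled that from regressing the three-visit mean, which confirms the equal weights. Mean model-based standard errors, shared against visit-specific, were 1.013 against 1.007 at R² 0.10 and 0.914 against 0.893 at R² 0.30. A further simulation gave power of 82.7% against 82.7% at R² 0.10 and 86.7% against 87.7% at R² 0.20. At R² of zero the empirical standard error was 1.049 either way.

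**The case against.** A reader might infer that the Week 24 adjustment is set mostly by Week 4 data and that most of the benefit of adjusting is thrown away. The documents do not support that. SAP 5.2.3 defines the model by formula, as a random subject effect plus error, and Protocol 9.4.2 and SAP 1.4 agree. Under that formula the visits count equally and at least 80% of the gain is kept in the patterns tried. Week 4 dominance needs a covariance that neither document specifies.

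The opposing case goes further:

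- **Covariate strength is unknown.** The stratification rationale is qualitative and concerns gain on an integrase-inhibitor regimen. Half the participants leave that regimen at Day 1, and all were selected for an earlier gain of at least 10%. Effects could also plateau early. This stands: every size above is conditional.
- **Stratified blocks already balance sex and race.** This stands for the point estimate. The model-based standard error still falls only if the model removes the Week 24 variance due to the strata, and BMI is not a stratification factor.
- **Nothing falls short of plan.** This stands. The sample size rests on an unadjusted t-test, every scenario is above its 80%, and re-estimation may raise the total to 150.
- **Changing the primary model late is not trivial.** This stands in part. The SAP amendment history for February 2022 cites feedback on interim outputs, and SAP 5.2.3 combines interim and final p-values.

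On the other side, the MMRM label with no stated covariance leaves room for an unstructured fit using these same main effects. In the two earlier studies the SD rose between Weeks 24 and 48, from 4.6 to 5.0 and from 4.0 to 5.1. That makes rising variance plausible, but it says nothing direct about Weeks 4 to 24.

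**Conclusion.** The point holds as a small loss of precision. The Week 24 contrast is adjusted by an average covariate effect over three visits instead of the Week 24 effect.

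Under the model as written and linear growth, the cost is under 1 power point at R² up to 0.10 and about 1 to 2 points at R² 0.20 to 0.30. It is smaller under square-root growth and zero if the effects are constant. Under visit-specific variances that rise over time, the cost with linear growth is about 2 to 3 points at R² 0.10 and 5 to 6 at R² 0.20. The SAP neither states nor rules out that fit.

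R², growth shape, dropout and covariance are all assumptions. The documents do not support reading this as bias, as an underpowered trial, or as a primary time point left essentially unadjusted. Severity: minor.

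**What to change.** In SAP 5.2.3, add Baseline BMI*Time, Sex*Time and Race*Time as fixed effects, so that the Week 24 least-squares means use Week 24 covariate effects. Apply the same model in SAP 5.2.4.

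The cost is two further coefficients for each of three covariates, six in all, on about 110 × 3 = 330 observations. No new data are needed and the estimand is unchanged. If the covariates are not prognostic, the loss is negligible.

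Because the trial is open-label and combines p-values across stages, the amendment should be fixed before the primary analysis, made without reference to weight results by arm, and should state which model produced the interim p-value. The new terms also make the Week 24 adjustment less dependent on the covariance chosen. They do not settle that choice, which the SAP should state separately.

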9.1. Statistical Hypotheses

The statistical hypothesis is the following:

 H_0 : Dt-Dc 0 versus H_1 : Dt -Dc \neq 0.

Where H_0 is the null hypothesis, H_1 is the alternative hypothesis; Dt %body weight change from baseline at Week 24 for treatment D/C/F/TAF, Dc for the Delayed Switch arm.

The statistical hypothesis will be tested using repeated measures longitudinal method (linear mixed-effects model) at 0.05 significance level, 2-sided.

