1. INTRODUCTION

This statistical analysis plan (SAP) contains definitions of analysis sets, derived variables and statistical methods for the analysis of metabolic (the percent change in body weight), efficacy and safety.

The primary study intervention is the darunavir/cobicistat/emtricitabine/tenofovir alafenamide (D/C/F/TAF) fixed-dose combination (FDC). D/C/F/TAF FDC is a 4-agent tablet for oral once-daily use for the treatment of human immunodeficiency virus (HIV)-1 infection in adults. This tablet contains the protease inhibitor (PI) darunavir (D or DRV) (800 mg), the pharmacokinetic (PK) enhancer cobicistat (COBI or C) (150 mg), the nucleoside reverse transcriptase inhibitor (NRTI) emtricitabine (FTC or F) (200 mg), and the tenofovir (TFV) prodrug tenofovir alafenamide (TAF) (10 mg). The D/C/F/TAF FDC tablet (SYMTUZA®) was approved by the US Food and Drug Administration as a complete regimen for the treatment of HIV-1 infection in adults and pediatric patients weighing ≥40 kg who have no antiretroviral (ARV) treatment history or who are virologically-suppressed (human immunodeficiency virus type 1 ribonucleic acid [HIV-1 RNA] less than 50 copies per mL) on a stable ARV regimen for at least 6 months and have no known substitutions associated with resistance to DRV or TFV. Participants not initially randomized to receive treatment with the D/C/F/TAF FDC will be assigned to maintain treatment on their baseline ARV regimen. The baseline ARV regimen in this study will be comprised of an INI + TAF/FTC ARV regimen.

The following analyses will be performed:

- An interim analysis at week 12 for monitoring purpose including an unblinded sample size reestimation and futility analysis (see also Section 3)
- The primary analysis: once all participants have completed the Week 24 assessments or discontinued earlier. The primary hypothesis will be tested at an overall significance level of 0.05, 2-sided in a longitudinal data with repeated measures model (Section 5.2.3). In this analysis, primary and other endpoints up to week 24 will be presented. Additionally, patient data collected beyond week 24 at this time, including metabolic, adverse events (AEs) and other pertinent data, will be descriptively summarized
- The Week 48 analysis: once all participants have completed the Week 48 assessments or discontinued earlier. Descriptive statistics will be conducted

1.1. **Trial Objectives**

1.1.1. **Primary Objective**

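### SAP 5.2.3 controls type I error with a combination p-value, but its only 95% CI comes from a different statistic, so a borderline interval can contradict the test

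*SAP*

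**What the plan says.** SAP 5.2.3 attaches two statistics to one null hypothesis.

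The first is the model contrast: "The statistical hypothesis will be tested by estimating the treatment LSmeans for the %change in body weight corresponding to the time measurement at week 24". Then comes "The significance level p-value and 95% confidence interval for the difference will be provided". On the data to be used, the section says "All available data from randomized participants that have received at least one dose is included (ITT analysis set) will be used for the analysis". Together these describe one MMRM fitted to both stages at once.

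The second follows directly: "To control for the overall Type I error rate at the 2-sided 0.05 significance level, the weighted inverse-normal p-value combination test will be used". The section continues "The overall p value will be calculated by the combination statistic below" and gives Z = w1·Φ⁻¹(1−p1) + w2·Φ⁻¹(1−p2), with w1 = √(n1/N) and w2 = √(n2/N).

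Elsewhere only the model is named. SAP 1 has "The primary hypothesis will be tested at an overall significance level of 0.05, 2-sided in a longitudinal data with repeated measures model" and Protocol 9.1 has "The statistical hypothesis will be tested using repeated measures longitudinal method". No section defines an interval or an estimate from the combination statistic. SAP 5.2.3 does not say whether n1, n2 and N are planned or realised, whether p1 and p2 are one-sided, or how to place participants who have only Week 12 data at the interim.

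**The concern.** The estimand in SAP 5.2.2 is a mean difference in percent weight change, so its interval will be a headline result. A reader expects a 95% CI that excludes zero to go with a two-sided p below 0.05. That holds when both come from one statistic. Here the pooled model weights participants by the information they contribute, while the combination test weights the stages by w1 and w2. The two are highly correlated but not identical, and they can fall on opposite sides of 0.05. The report would then show a primary p-value and a primary interval that disagree, with no planned way to present them.

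**Working it through.** **Inputs.** From SAP 1.5: 80% power, two-sided 0.05, difference 3%, effect size (ES) 0.54, 55 per arm, maximum total 150. From SAP 3: interim at about 60% of 110 (66 participants) with Week 12 and about 30% (33) with Week 24. Protocol 9.6 plans no early stop for superiority, so the final critical value is 1.96. The SD implied by the plan is 3/0.54 = 5.56.

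**The plan's own figure.** 16/0.54² = 54.9, which rounds up to 55 per arm. The exact t-test solution is 54.8, and power at 55 per arm is 80.1%. The sample size is reproduced at two-sided 0.05.

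**Worked examples.** Assumptions: stage 1 n = 66, N raised to the cap of 150, planned weights 0.6/0.4, and stage p-values pointing in one direction. With known variance:

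- Combination: Z = √0.6·z1 + √0.4·z2 = 0.7746·z1 + 0.6325·z2
- Pooled: Z = √(66/150)·z1 + √(84/150)·z2 = 0.6633·z1 + 0.7483·z2, with SE = 2×5.56/√150 = 0.907
- Inverted CI: the stage SEs are 2×5.56/√66 = 1.368 and 2×5.56/√84 = 1.212. The combined statistic at a shift d is Z − d(0.7746/1.368 + 0.6325/1.212) = Z − 1.088d. The limits are therefore (Z ± 1.96)/1.088.

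| | z1, z2 | Combination Z, p | Pooled Z, p | Pooled 95% CI | Inverted 95% CI |
|---|---|---|---|---|---|
| A | 1.0, 1.8 | 1.913, 0.056 | 2.010, 0.044 | 0.05 to 3.60 | −0.04 to 3.56 |
| B | 1.8, 1.0 | 2.027, 0.043 | 1.942, 0.052 | −0.02 to 3.54 | 0.06 to 3.66 |

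Differences are in percentage points, with positive values favouring Immediate Switch. In A the pooled interval excludes zero and the combination test does not reject. In B it is the reverse. The inverted interval agrees with the test in both, and is 3.92/1.088 = 3.60 wide against 3.92×0.907 = 3.56, about 1% wider.

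**How often.** Share of simulated trials in which the two results fall on opposite sides of 0.05. The first three rows use stage-wise t-tests with 33 per arm in stage 1 and every Week 24 weight observed. The fourth is a normal-theory calculation.

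| Setting | ES 0.54 | ES 0.40 |
|---|---|---|
| N=110, weights 0.6/0.4, disjoint complete stages | 1.3% | about 2% |
| N=150, planned weights 0.6/0.4 | 2.2–2.4% | 4.7–5.0% |
| N=150, realised weights 0.44/0.56 | about 0.7% | 1.3–1.4% |
| N=110, p1 frozen at the interim cut | 10–18% | 13–20% |

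With known variance and realised weights the two formulas are the same, so the discordance is zero. What remains in the first and third rows comes from stage-wise variance estimation.

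The last row takes the stage 1 variance as 4σ²((1−r²)/33 + r²/66), with an assumed Week 12–Week 24 correlation r of 0.5 to 0.85. The combination then omits Week 24 weights that stage 1 participants supply later, and the pooled model includes them. A separate three-visit model with correlation 0.5 to 0.9 gave 7–17% at ES 0.54 and 9–19% at ES 0.40.

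The disagreement is concentrated near the boundary. When the pooled p is between 0.03 and 0.05, the combination test fails to reject in about 11–13% of trials at N=110. At N=150 it fails in about 30–34% with planned weights and 9–10% with realised weights.

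**Coverage.** Under three assumed re-estimation rules with N between 110 and 150, the pooled CI covers 94.7–95.1%. In a separate calculation, a rule that goes to 150 whenever conditional power is below 0.8 gave the pooled test a type I error of 5.6%, that is, coverage of 94.4% at zero effect. Restricting the increase to conditional power of 0.3 to 0.8 gave 4.8%.

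**The case against.** The strongest reply is that the deciding statistic can be identified. SAP 5.2.3 ties error control to the combination test and calls its result the overall p-value, while the model p-value is merely to be provided. That is a fair reading, and it stands. A reader might infer that two statisticians could follow different sentences and declare different primary results. The documents do not support going that far, although the sentence saying the LS-mean contrast tests the hypothesis should not be left to compete.

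A second reply is that Protocol 9.2 and 9.6 and SAP 1.5 and 3 defer protection of the significance level to the interim plan, the DRC charter or the DRC SAP. Those are not available here and may fix the weights and stage p-values. But the deferral does not mention the final interval or estimate, and SAP 5.2.3 is where the final analysis is set out.

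A third is that the larger percentages depend on choices the plan does not make. This also stands: 150 is only a cap, no passage says the sample size was raised, and neither planned weights nor a frozen stage 1 p-value is stated.

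Finally, a reader might suppose that the interval is to be judged against 3%. That figure is a sample-size input described as clinically meaningful, and no section compares the CI with it.

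**Conclusion.** The point holds in a narrow form. The interval and estimate in SAP 5.2.3 do not belong to the test that controls the error rate, so a borderline trial can report a CI that contradicts its deciding p-value. The size is about 1–2% of trials at N=110 with disjoint complete stages and about 1–5% at N=150 depending on the weights. It is about 10–20% at ES 0.40–0.54 only if p1 is frozen at the interim cut. These figures assume one-directional stage p-values and, for the last, a within-person correlation of 0.5 to 0.85.

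It would be tempting to call the pooled CI invalid after an unblinded re-estimation. The calculations do not show that: coverage stays close to 95% under the assumed rules, though the actual rule is not in these documents. The defect is inconsistency between test and interval, confined to borderline results. It is still worth correcting, because it concerns a stated primary analysis and is cheap to remove.

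**What to change.** In SAP 5.2.3, with a cross-reference from SAP 1 and 1.4:

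- State that the overall combination p-value alone decides the primary hypothesis at 0.05 two-sided.
- Define the primary 95% CI as the set of differences d that the same combination test, applied to stage-wise MMRM estimates shifted by d, does not reject.
- State what that inversion requires: directional stage-wise p-values, weights fixed at the planned fractions, and disjoint stage cohorts with each participant assigned to one stage.
- Keep the pooled MMRM estimate, p-value and CI as supportive, labelled as not adjusted for the sample-size re-estimation.

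The point estimate can be left to the sponsor; the median-unbiased value from the same inversion is one option.

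The cost is some SAP wording, including the three conditions above, and a short program, with no extra data or participants. The downside is a slightly wider interval, about 1% in the worked examples. Realised weights would remove most of the disagreement without inversion, but weights that move with the re-estimation do not give the error control the combination test is there to provide.

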3. INTERIM ANALYSIS AND, DATA MONITORING COMMITTEE REVIEW

An interim analysis (IA) is planned when approximately 60% of the initial planned 110 participants have completed the Week 12 visit and approximately 30% of participants have completed the Week 24 visit to re-estimate the sample size to ensure adequate power for the hypothesis testing. All cumulative data will be used for the interim analysis. Details for the sample size re-estimation (SSR), threshold for the conditional power, and protection of overall significance level will be provided in DRC charter for the IA and monitoring. The planned maximum total sample size after SSR is 150 participants. IA contents will be defined in DPS.

The Data Monitoring Committee (DMC) is not applicable. Instead, a data review committee (DRC) is used for the interim analysis. Details are included in the DRC charter.

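### SAP 5.2.3 does not fix the combination-test weights in advance; read literally they move with the unblinded sample-size re-estimation, so the claimed 5% type I error is not guaranteed

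*SAP*

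**What the plan says.** SAP 5.2.3 gives the purpose of the method as "To control for the overall Type I error rate at the 2-sided 0.05 significance level" and the means as "the weighted inverse-normal p-value combination test will be used to combine p-values from interim stage and primary analysis stage". The statistic is Z = w1·Φ⁻¹(1−p1) + w2·Φ⁻¹(1−p2), with w1 = √(n1/N) and w2 = √(n2/N), where "n_1 and n_2 are number of subjects in IA stage and remaining primary stage". N is not defined and no numerical weights appear.

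SAP 1.5 and 3 and Protocol 9.2 and 9.6 describe one unblinded interim analysis. It takes place when about 60% of the planned 110 participants have completed Week 12 and about 30% have completed Week 24. Sample size may then be raised by a conditional-power approach, and "The planned maximum total sample size after SSR is 150 participants". The conditional-power threshold and the protection of the significance level are left to the DRC charter (SAP 3) or to the DRC charter and DRC SAP (Protocol 9.6). Neither document was available for this review. Protocol 9.6 also says that early stopping for superiority is not intended.

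On reporting, SAP 5.2.3 says "The significance level p-value and 95% confidence interval for the difference will be provided". It does not link that interval to the combination statistic.

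**The concern.** An inverse-normal combination test keeps its level under any re-estimation rule only if the weights are set before the interim result is used. The stage-2 z-score is standard normal under the null whatever stage-2 size is chosen, so a weighted sum with constant weights is also standard normal. If the weights are recomputed from the stage-2 size actually recruited, they become a function of the interim z-score and the argument fails. The statistic is then the ordinary pooled z-test, with no correction for the adaptation.

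This is the trial's only confirmatory test, and the formula is there specifically to protect its level. A reader of SAP 5.2.3 cannot tell whether it does. Nor can the weights be computed by assuming planned values, because planned n1 could be 66 (Week 12 completers) or 33 (Week 24 completers).

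**Working it through.** **Inputs.** Two-sided alpha 0.05 (SAP 5.2.3). Planned total 110, 55 per arm, effect size 0.54 (SAP 1.5). Maximum total 150 (SAP 3). Stage 1 size either 60% × 110 = 66 or 30% × 110 = 33. Critical value 1.96, because no early efficacy stop is intended (Protocol 9.6).

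**The plan's own figure.** The sample size is set out as "Using a T-test with 80% power to detect a difference of 3% at the significance level of 0.05, 2-sided" with n per arm = 16/ES². At ES = 0.54 this gives 16/0.2916 = 54.9, so 55 per arm. The exact t-test gives 54.8, with 80.1% power at 55. The planned size reproduces.

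**Weights under the two readings.**

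| | n1 = 66 | n1 = 33 |
|---|---|---|
| Planned, N = 110 | √(66/110) = 0.775; √(44/110) = 0.632 | √(33/110) = 0.548; √(77/110) = 0.837 |
| Realised, N = 150 | √(66/150) = 0.663; √(84/150) = 0.748 | √(33/150) = 0.469; √(117/150) = 0.883 |

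**Type I error if the weights follow the realised sizes.** Given the interim z1 and a chosen n2, the null rejection probability is

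1 − Φ((1.96 − w1·z1)/w2) + Φ((−1.96 − w1·z1)/w2).

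This is averaged over z1 ~ N(0,1), with total N between 110 and 150. The upper bound takes, at each z1, the n2 that maximises the expression. The conditional-power (CP) rules use the current trend,

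CP = 1 − Φ((1.96√N − z1√n1)/√n2 − (z1/√n1)·√n2),

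and raise N when CP at N = 110 lies between the lower threshold and 80%. N goes up either until CP reaches 80% (capped at 150) or straight to 150. CP is taken either in the hypothesised direction only or for a trend in either direction. Ranges cover these variants.

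| Rule, realised weights | n1 = 33 | n1 = 66 |
|---|---|---|
| Worst choice of n2 at every z1 | 5.40% | 5.75% |
| No lower threshold, hypothesised direction | 5.2% | 5.3% |
| No lower threshold, either direction | 5.4% | 5.6% |
| Lower threshold 10% | 5.1% | 5.0–5.1% |
| Lower threshold 20% | 5.0% | 4.9–5.0% |
| Lower threshold 30% | 5.0% | 4.8–4.9% |

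**With planned weights.** The two-sided error is 5.0% under every rule, given independent stages. A simulation of 4 million trials with weights 0.775/0.632 gave 5.01%.

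**Cost of fixed weights when N = 150 and n1 = 66.** At ES 0.54, power is 0.904 with fixed weights against 0.911 pooled: 0.911 − 0.904 = 0.007, or 0.7 points.

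**Agreement of test and interval.** In the same setting, the fixed-weight test and an ordinary pooled 95% interval disagree on significance in about 1.5% of trials at ES 0, 5% at ES 0.3 and 2.2% at ES 0.54.

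**The case against.** The SAP never says the stage sizes are the realised ones. Its wording fits planned sizes with N = 110 equally well, and on that reading the method has the property claimed for it. Alpha protection is explicitly assigned to the DRC charter and DRC SAP, which may already state fixed weights. The larger error figures also need behaviour that the plan does not describe. The bound requires n2 to be chosen adversarially at every interim value, and a rule with no lower threshold would raise N when conditional power is near zero, which sits badly with the futility evaluation in Protocol 9.6. With any lower threshold of 10% or more the effect is about 0.1 point or less.

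All of this stands, and it limits the point. A reader might infer that the SAP prescribes realised weights, or that the trial's type I error is 5.75%. The documents support neither: the first is the literal reading of an undefined term, and the second is an upper bound under that reading. What remains is that the section defining the confirmatory test admits two readings, only one of which controls the level under any re-estimation rule, and the threshold that would settle the size of the effect is not in these documents.

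A reader might also infer that fixed weights alone secure exactly 5%. They do not. The stage-wise p-values must also be independent, and the interim uses all cumulative data, including participants with Week 12 but not yet Week 24 weights.

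**Conclusion.** The point holds as a gap in specification. Under the literal reading it is an error in the stated rule; under the planned-size reading it is not. Type I error control cannot be verified from SAP 5.2.3. The possible excess over 5% is at most 0.4 points (n1 = 33) or 0.75 points (n1 = 66), and it is negligible or absent if increases are limited to conditional power of roughly 20% or more.

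These figures assume the normal approximation, one-sided stage p-values that are independent under the null, equal information per participant, non-binding futility, no reduction below 110 and the 150 cap.

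Timing matters too. The SAP was approved on 24 March 2023, and its amendment history gives interim analysis outputs as a reason for a February 2022 change. This suggests that the interim came first. Numbers entered now do not by themselves show that the weights were set beforehand, so they need to be traced to a pre-interim document.

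The confidence interval is a smaller, related matter: with fixed weights and a raised N, an ordinary MMRM interval can contradict the test.

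**What to change.** In SAP 5.2.3, state the numerical weights from the planned stage sizes with N = 110: 0.775 and 0.632 if planned n1 is 66, or 0.548 and 0.837 if it is 33. Name which applies. Take the values from the DRC charter or DRC SAP in force before the interim, and cite that document and its date. Add that the weights do not change if the re-estimation raises N or if stage sizes differ from plan. Note that exact 5% control also requires independent stage-wise p-values.

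Report the Week 24 difference with a confidence interval obtained by inverting the weighted statistic, and give the ordinary MMRM interval as supportive.

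The cost is a few sentences and a check against the DRC documents, plus about 1 point of power if N goes to 150. There is no power cost if N stays at 110 and the stages are as planned.
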